6.7 Outcomes

6.7.1 Primary outcome

The primary outcome is a binary measure of the onset of one or more new pulmonary complications within five days of randomisation. This will be adapted from the outcome proposed by the European Society of Anaesthesiology and Intensive Care Medicine as a consensus definition (Table 2) (23). Patients with evidence of pulmonary complications prior to randomisation will not meet the primary outcome. Any deaths occurring within the first 5 days following randomisation will meet the criteria for the primary outcome.

Table 2: Pulmonary Complications

Complication	Definition
Respiratory Infection	Patient has received antibiotics for a suspected respiratory infection and met one or more of the following criteria: new or changed sputum, new or changed lung opacities, fever, white blood cell count $>12 \times 10^9 \text{ l}^{-1}$

Respiratory failure	PaO ₂ <8kPa (60mmHg) on room air, a PaO ₂ :FiO ₂ ratio <40kPa (300mmHg) or arterial oxyhaemoglobin saturation measured with pulse oximetry <90% (or <88% for patients with known chronic respiratory disease) and requiring oxygen therapy
Pleural effusion	Chest radiograph demonstrating blunting of the costophrenic angle, loss of sharp silhouette of the ipsilateral hemidiaphragm in upright position, evidence of displacement of adjacent anatomical structures or (in supine position) a hazy opacity in one hemithorax with preserved vascular shadows
Atelectasis	Lung opacification with a shift of the mediastinum, hilum or hemidiaphragm toward the affected area, and compensatory over-inflation in the adjacent non-atelectatic lung
Pneumothorax	Air in the pleural space with no vascular bed surrounding the visceral pleura
Bronchospasm	Newly detected expiratory wheezing treated with bronchodilators
Aspiration pneumonitis	Acute lung injury after the inhalation of regurgitated gastric contents

Primary outcome data will be collected by research practitioners from inpatient hospital records at five days and reviewed/confirmed by the local Principal Investigator. For the small number of patients discharged in the interim, online GP records (routinely available at recruiting sites) will be checked for evidence of pulmonary related events (e.g., pneumonia).

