6.7.2 Secondary outcomes

- Patient reported breathlessness at baseline and 5 (+2*) days (The Dyspnea-12 Questionnaire)
- Patient reported pain at baseline and 5 (+2*) days (Numeric Pain Rating Scale)
- Length of initial stay up to 30 days post randomisation
- Admission to Critical Care up to 30 days post randomisation
- Mortality up to 30 days post randomisation
- Hospital readmission within 30 days of randomisation

*Pain and breathlessness scores will be collected on day 5 where possible but a +2-day window will be accepted to accommodate lack of weekend staffing.

It is anticipated that the majority of patients will remain inpatients on day 5 and patient reported outcome measures can be collected in person by local site staff. For any patients discharged prior to day 5, follow-up can be completed remotely by telephone. The Dyspnea-12 questionnaire and Numeric Pain Rating Scale are both possible to complete by telephone. The researcher will make (up to) three contact attempts. If no response is received, the questionnaires will be marked as missing.

As the Dyspnea-12 Questionnaire includes a question pertaining to depressive symptoms, any participant identified as indicating severe levels of depression will be encouraged by local site staff to seek further evaluation or support from their treating clinician or General Practitioner.

The NPRS has been reported suitable to use with people with mild to moderate cognitive impairment (²⁴). We are unable to find a breathlessness patient reported outcome, suitable for trauma, that has been validated for cognitive impairment in this population. It is recognised that some data for this secondary outcome may be missing for those with mild to moderate cognitive impairment. However, “here and now” symptom self-reporting tools have been shown to be valid and reliable in persons with mild cognitive impairment in previous literature (²⁵) and use of the dyspnea-12 questionnaire in this

trial is supported by our patient and public involvement representatives. Secondary outcomes measured up to 30 days post randomisation will be collected by research staff from their hospital's electronic patient record.

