7.3 Screening and identification of participants

Hospital staff will be asked to complete a trial-specific screening Case Report Form (CRF) for each patient aged ≥ 65 years admitted to that hospital with acute rib fracture(s) following blunt chest wall trauma.

Recruitment will be undertaken 24 hours a day, 7 days a week. Potentially eligible participants will be identified by clinical staff or research delivery staff (e.g. Research Nurses/Physiotherapists) at the time of arrival in ED or on/after transfer to inpatient settings (e.g. ward, acute medical/surgical assessment unit). Upon identifying a (potentially) eligible patient, a member of the clinical team or research practitioner will give the patient the written study Summary Participant Information Sheet (Summary PIS) and, where appropriate, the full Participant Information Sheet (Detailed PIS) (e.g. the patient has read the Summary PIS and requested further information and/or is suitably comfortable and able to read both documents at that time). We recognise that our target population is older adults. Patient information materials will therefore be available in a variety of formats, including paper (normal and large print) and video, as advised by our patient groups to maximise participation across all potentially eligible patients.

Patients will be given sufficient time to read/view the information material and ask any questions they may have about the trial. The length of time patients will have to consider participation will vary due to the nature of EDs and assessment pathways. If appropriate, consent can be received whilst the patient is still within the ED, however consent will not be taken until immediate care needs have been addressed. When considering participation in the emergency setting, patient consideration-time is estimated to be from one to four hours; this approach is considered acceptable by patients, as demonstrated by other ED-based research undertaken by our group (^{5,26}). If required, the participant can be given longer to consider involvement even if transferred to a ward. However, due to the need for early intervention, a maximum of 24 hours from admission to randomisation will be set (and written consent must be received prior to randomisation).

In patients without capacity, we will seek approval from a patient's personal consultee/legal representative (see section 7.6)

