In England, Wales and Northern Ireland a personal consultee will be presented with the Summary Participant Information Sheet or equivalent video and, where appropriate, the Detailed PIS. Based on the study information, the Consultee will provide advice about whether the individual would wish to be included in the study or not. A patient will only be enrolled via personal consultee approval if the consultee is available to provide approval within 24 hours of the patient's admission to hospital and reasonable support with IS training/use.

In Scotland a Personal Legal Representative (PLR) will be approached and presented with the Personal Legal Representative Summary PIS or equivalent video, and supporting Detailed PIS, and will provide advice about whether the individual would wish to be included in the study or not. A Personal Legal Representative can be a Welfare Guardian or Welfare Attorney, or the patient's nearest relative. If a PLR is not available, the participant will not be enrolled.

Patients where capacity is regained within 5 days of randomisation: patient's who have regained capacity (confirmed as ≥ 48 hours) will be approached by a member of the research team and provided with information about the study that will explain what has (likely) happened so far. If day 5 post-randomisation falls on a weekend, assessment will be completed on the following working day. Patients will be asked to provide consent to continue in the study; they may wish to continue active involvement in the study (e.g. will complete questionnaires) or passive involvement (e.g. no questionnaires but allow continued access to medical records only). If a patient decides that they do not wish to continue in the study, their ongoing participation will stop; however, data collected up to this point will be retained and analysed.

It is possible that patients may lose capacity again, after agreeing to remain in the study. In this case, we will consider the original consultee/PLR consent to remain valid. Staff will inform the consultee/PLR, who will retain the right to withdraw the person they provided consent for at any time.

A summary of the various study invitation and consent pathways and documentation are shown in Figure 1 below.

[figure not shown]
[figure not shown]

Figure 1: Approach and consent pathways

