For patients who have mild/moderate cognitive impairment (e.g. due to Alzheimer's disease), the PROMs may be completed with the assistance of a researcher/member of the clinical team (or person with caring responsibility if/where feasible); if in such participants it becomes unfeasible to complete the PROMS (or elements of it), site staff should record this in the 5-day CRF.

Participants who have transferred to a different hospital or who have been discharged from hospital at 5-days post-randomisation (+2 days):

Follow up will be completed remotely using a range of available methods to suit the participant's preferences and location (e.g. via telephone or site staff at receiving hospital if transferred to another trial site). If the participant does not have capacity, where possible, then a consultee (and/or person with caring responsibility) will be asked to assist the participant to complete the PROMS. If it is not feasible for the participant to complete (part of) the PROMs, site staff should record this in the 5-day CRF.

7.11 Follow up Data Collection at Day 30

CRF (site staff): A delegated site staff member will complete the 30-day CRF. Data capture on this CRF will include (but is not limited to):

- Hospital admission details, including discharge status and date (where applicable)
- Mortality data
- Resource use e.g. admission to critical care (including HDU) during index admission; any unplanned readmissions within 30 days

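### Primary-outcome extraction is set at day 5, with day 5 not defined in hours and no post-window extraction date or look-back, so late or slowly documented events may be missed

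*Protocol*

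**What the plan says.** Protocol section 6.7.1 defines the endpoint by onset: "The primary outcome is a binary measure of the onset of one or more new pulmonary complications within five days of randomisation". The collection instruction in the same section is "Primary outcome data will be collected by research practitioners from inpatient hospital records at five days and reviewed/confirmed by the local Principal Investigator". For participants discharged earlier, "online GP records (routinely available at recruiting sites) will be checked for evidence of pulmonary related events (e.g., pneumonia"), with no date given for that check.

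The schedule in section 7.8 puts the primary outcome in the Day 5 column. The patient-reported outcomes have their own Day 5(+2) column, and section 6.7.2 gives the reason: "Pain and breathlessness scores will be collected on day 5 where possible but a +2-day window will be accepted to accommodate lack of weekend staffing". Section 7.6 makes a similar allowance for the assessment of participants who regain capacity: "If day 5 post-randomisation falls on a weekend, assessment will be completed on the following working day". Section 6.6.5 has adherence diaries collected on or after day 5, or at discharge if that is sooner. No such allowance is written for the primary outcome.

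Section 7.3 states: "Recruitment will be undertaken 24 hours a day, 7 days a week". Section 7.11 provides for a later record review ("A delegated site staff member will complete the 30-day CRF"). Its list covers admission, mortality and resource use, is expressly not exhaustive, and does not mention pulmonary complications.

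**The concern.** The event window and the date on which the notes are read are two different things, and the protocol gives only one number, five days, for both. Day 5 could mean the fifth calendar day after randomisation or the completion of 120 hours. Under the first reading, a participant randomised at 20:00 whose notes are read at 10:00 on day 5 has been at risk for 110 hours, so the last 10 hours are not searched.

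Documentation lag adds to this. In Table 2, respiratory infection needs antibiotics plus a second finding, and several other components rest on imaging. For an onset on day 4 or 5, the report, blood result or GP entry may not yet be in the record on day 5.

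An event missed in this way would most naturally be recorded as no complication, not as missing. The 10% attrition allowance in section 6.7.4 is justified by inaccessible GP records, and the sensitivity analysis in section 11.1 concerns missing data, so neither covers it. Section 10.4 says that source data are not routinely compared with the database, so central monitoring is unlikely to find it. Nor can an analysis plan recover events that were never extracted. Sites may also read the instruction differently, which would make the length of follow-up for the primary endpoint vary between them.

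**Working it through.** **1. The plan's own figure.** Inputs from section 6.7.4: 50% v 30%, 90% power, 5% alpha (two-sided, which reproduces the result), 10% attrition; 1:1 allocation from section 7.7.

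n per arm = [1.960·√(2·0.40·0.60) + 1.2816·√(0.50·0.50 + 0.30·0.70)]² / 0.20² = 124.0, so 124 per arm and 248 in total. 248/0.90 = 275.6, so 276. Both stated figures reproduce.

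**2. How early day-5 extraction can be.** With randomisation on day 0, calendar day 5 starts between 96 and 120 hours after randomisation. The shortfall is therefore at most just under 24 hours. It is zero for anyone randomised at an earlier clock time than that at which the notes are read. If reading starts at 09:00 (an assumption), the largest shortfall is 15 hours, for randomisation at midnight.

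**3. Events lost.** The documents give no timing of onsets. Assume a constant hazard in each arm that yields 50% and 30% at 120 hours. The proportion with onset by hour t is then 1 − 0.5^(t/120) for control and 1 − 0.7^(t/120) for intervention.

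- 12 hours early (t/120 = 0.9): 46.4% and 27.5%. Share of events lost: 7.2% (control) and 8.5% (intervention).
- 24 hours early (t/120 = 0.8): 42.6% and 24.8%. Share lost: 14.9% and 17.3%.

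**4. Power at 124 per arm.** Power = Φ(z), with z = [|p1 − p2|·√n − 1.960·√(2p̄(1 − p̄))] / √(p1(1 − p1) + p2(1 − p2)).

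| Extraction | Control | Intervention | Difference (points) | Odds ratio | z | Power |
|---|---|---|---|---|---|---|
| After 120 h | 50.0% | 30.0% | 20.0 | 0.43 | 1.282 | 90.0% |
| 12 h early | 46.4% | 27.5% | 19.0 | 0.44 | 1.155 | 87.6% |
| 24 h early | 42.6% | 24.8% | 17.7 | 0.45 | 1.013 | 84.5% |

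These rows apply the shortfall to every participant, which overstates its effect, and leave out reporting lag, which understates the total loss.

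**The case against.** The strongest reply is that the endpoint is anchored to onset, so the date on which the notes are read does not alter its meaning. On that view, at five days and the Day 5 column name the outcome time point, just as readmission sits under Day 30. The contrast with the patient-reported outcomes then proves less than it seems to: those are answered as the participant feels at that moment, so they need a stated tolerance, whereas a chart review does not. There are also routes for late information. The local Principal Investigator's confirmation and the GP check carry no closing date, data cleaning continues throughout the trial (section 9.2), adverse events are assessed to day 30 (section 8.3), and mortality is collected again at day 30.

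Much of this stands. A reader might infer that the search closes on day 5 and that anything documented later is scored as no complication. The protocol says neither. A reader might also infer that a 24-hour shortfall loses a fifth of events and takes power to about 77%. That requires onsets spread evenly over the five days; under a constant hazard the loss is 15% to 17%. Nor does any section suggest that extraction timing will differ by arm. Local teams are unblinded (section 7.12), so it could, but that is a possibility and not a finding.

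What the reply does not remove is the literal instruction. None of these routes requires the primary outcome to be re-checked, and a site that extracts on the morning of day 5 is following the protocol as written. The weekend-staffing reason ("a +2-day window will be accepted to accommodate lack of weekend staffing") may apply equally to staff who read records, yet no rule covers a day 5 that falls on a weekend.

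**Conclusion.** The point holds as a defect in how the timing of ascertainment is fixed. The protocol sets extraction at day 5, leaves day 5 undefined in hours, and gives no post-window date or look-back. Late or slowly documented events may therefore be missed and entered as absent. Equal under-ascertainment would pull the absolute difference towards zero and cost power; the odds ratio would move little.

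The size cannot be derived from the documents. The illustration (a loss of about 2 points of power at 12 hours and 5 to 6 points at 24 hours) rests on a constant hazard and on every participant being extracted early. Calendar day 5 makes 24 hours the ceiling for early extraction, and participants read on time or after a weekend would have no shortfall. Reporting lag would add an amount that the documents do not allow one to estimate. The stated sample size of 248, or 276 with attrition, is correct on its own assumptions.

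**What to change.** In section 6.7.1 and the schedule in section 7.8, separate the event window from the extraction date:

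- Keep onset within five days of randomisation, and define it as 120 hours from the time of randomisation.
- State that hospital and GP records are extracted only after that window has ended, for example from day 7 by using the +2 allowance that already exists, and in the same way in both arms.
- Record the date and time of onset for each component, so that later extraction cannot bring in events that began after 120 hours.

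A further look at onsets up to 120 hours when the 30-day CRF is completed is optional. It would catch slow reports and GP entries, but re-reading imaging, blood results and GP records is additional work for sites.

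The cost is slightly later completion of the primary-outcome form and a small amount of extra data entry. The endpoint definition in days, the sample size and the analysis model do not change.

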6.7.2 Secondary outcomes

- Patient reported breathlessness at baseline and 5 (+2*) days (The Dyspnea-12 Questionnaire)
- Patient reported pain at baseline and 5 (+2*) days (Numeric Pain Rating Scale)
- Length of initial stay up to 30 days post randomisation
- Admission to Critical Care up to 30 days post randomisation
- Mortality up to 30 days post randomisation
- Hospital readmission within 30 days of randomisation

*Pain and breathlessness scores will be collected on day 5 where possible but a +2-day window will be accepted to accommodate lack of weekend staffing.

It is anticipated that the majority of patients will remain inpatients on day 5 and patient reported outcome measures can be collected in person by local site staff. For any patients discharged prior to day 5, follow-up can be completed remotely by telephone. The Dyspnea-12 questionnaire and Numeric Pain Rating Scale are both possible to complete by telephone. The researcher will make (up to) three contact attempts. If no response is received, the questionnaires will be marked as missing.

As the Dyspnea-12 Questionnaire includes a question pertaining to depressive symptoms, any participant identified as indicating severe levels of depression will be encouraged by local site staff to seek further evaluation or support from their treating clinician or General Practitioner.

The NPRS has been reported suitable to use with people with mild to moderate cognitive impairment (²⁴). We are unable to find a breathlessness patient reported outcome, suitable for trauma, that has been validated for cognitive impairment in this population. It is recognised that some data for this secondary outcome may be missing for those with mild to moderate cognitive impairment. However, “here and now” symptom self-reporting tools have been shown to be valid and reliable in persons with mild cognitive impairment in previous literature (²⁵) and use of the dyspnea-12 questionnaire in this

trial is supported by our patient and public involvement representatives. Secondary outcomes measured up to 30 days post randomisation will be collected by research staff from their hospital's electronic patient record.

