3 TRIAL SUMMARY

Trial Title	Randomised Evaluation of incentive Spirometry in OLder adults with rib fractures to preVEnt pulmonary complications	
Short title	RESOLVE	
Chief Investigator	[name]	
Joint Lead	[name]	
Sponsor	North Bristol NHS Trust (R&D)	
Funder	National Institute for Health and Care Research (NIHR) Research for Patient Benefit (RfPB) Programme	
Trial Design	Prospective multicentre parallel group randomised controlled superiority trial	
Trial Participants	Adults aged ≥ 65 years presenting to UK Emergency Departments with traumatic rib fracture(s)	
Target sample size	276	
Target number of study sites	12	
Intervention	Incentive spirometry (and usual care)	
Treatment duration	Minimum 72 hours	
Inclusion criteria	
 • Aged ≥ 65 years • Radiological evidence of acute rib fracture(s) • Planned for admission • Has capacity to provide informed consent or personal consultee/legal representative available and able to support use of incentive spirometer 	
Exclusion criteria	
 • Co-existing injury or condition for which treating clinician deems patient unable to use incentive spirometer (e.g. facial injuries; burns to both hands; advanced dementia) • Patients who have SpO₂ <92% on air at time of screening (<88% for known chronic lung disease) • Intubated • Haemodynamic instability (e.g severe hypo- or hypertension, significant atrial/ventricular arrhythmia) • History of eye, inner ear or brain surgery within previous four weeks (Contraindication to using incentive spirometry) • 	
	Objectives	Outcome measures
Primary outcome	Onset of new pulmonary complications within 5 days of randomisation	Patient medical notes/EPR (see 6.6.1 for further detail) GP records*

Secondary outcomes	Patient reported breathlessness at 5 days (+2)	The Dyspnea-12 Questionnaire
	Patient reported pain at 5 days (+2)	Numeric Pain Rating Scale
	Length of stay up to 30 days post randomisation	Patient medical notes/EPR
	Admission to Critical Care/ICU up to 30 days post randomisation	Patient medical notes/EPR
	Mortality up to 30 days post randomisation	Patient medical notes/EPR
	Hospital readmission rates up to 30 days post randomisation	Patient medical notes/EPR
Internal pilot	Internal pilot progression criteria will be reviewed after 4 months of active recruitment. See section 6.3 for further detail.	

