Study duration	Grant contract start date: 01 August 2025 Anticipated duration: 26 months Anticipated end date: 30 th September 2027	

*For the small number of patients discharged within 5 days of randomisation, GP records will be checked for antibiotic prescription for pulmonary related events

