6.7.3 Hospital transfers

Should a participant be transferred to another hospital prior to primary and secondary outcome data collection, their participation in the trial will be ongoing and the initial recruiting site will remain responsible for remote follow-up with participants and the receiving site (where necessary).

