6.7.4 Target sample size (with calculation/justification)

276 patients recruited from 12 UK hospitals. The incidence of pulmonary complications in this population has been observed at 50% (5). In the only RCT of incentive spirometry for trauma identified, Sum and colleagues (8) observed a 50% absolute risk reduction in pulmonary complications, but this effect size was estimated with a large margin of error and may not be generalisable. A more conservative estimate of a 20% reduction in the intervention arm has, therefore, been proposed as a target effect size that is both achievable and meaningful to detect. Our PPI group agree this is a reasonable effect size to change practice. To detect a reduction in pulmonary complications from 50% in the control group to 30% in the intervention group with 90% power at a 5% alpha level, an analytical sample size of 248 is required. To allow for 10% attrition a total sample size of 276 is required. Most participants will remain inpatients at five days, and GP online records are routinely available for any that have been discharged. The only anticipated loss to primary outcome follow-up will be those who are admitted out of area and discharged within five days to another region where GP records may not be accessible. Sample size calculation was conducted using the 'power' command in Stata (version 18).

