9.3 Data collection

9.3.1 Data Sources

A full list of source data and location will be maintained in the Data Management Plan (DMP). Hospital records and GP records will also form part of the source data for this trial.

Data will be collected using electronic/paper case report forms (CRFs). Direct data entry to eCRFs will be done using REDCap, if paper CRFs are used these will be entered into the database as soon as possible.

Participant questionnaires will either be completed on paper (with data entered into the REDCap database by trial staff) or through an email link sent to the participant (data saved directly to the REDCap database).

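### For participants discharged home, the protocol names no source beyond the recruiting hospital's record for death and readmission to day 30, so events elsewhere can go unseen

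*Protocol*

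**What the plan says.** Section 6.7.2 fixes the source of the day-30 outcomes: "Secondary outcomes measured up to 30 days post randomisation will be collected by research staff from their hospital's electronic patient record". The trial summary (section 3) agrees. It gives patient medical notes or the EPR as the only source for "Mortality up to 30 days post randomisation" and for "Hospital readmission rates up to 30 days post randomisation". The asterisk for GP records in that table is attached to the primary outcome alone, and its footnote covers patients discharged within five days: "GP records will be checked for antibiotic prescription for pulmonary related events".

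Section 6.7.1 repeats that arrangement for the primary outcome. For patients discharged before day 5, "online GP records (routinely available at recruiting sites) will be checked for evidence of pulmonary related events".

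At day 30 a site staff member completes a CRF covering discharge status, mortality, critical care during the index admission, and any unplanned readmission (section 7.11). The schedule in section 7.8 shows no participant questionnaire at day 30.

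Two other places bear on the point. The Hospital transfers section (6.7.3) keeps the recruiting site responsible for follow-up with a transferred participant and the receiving hospital. Section 9.3.1 says in general terms: "Hospital records and GP records will also form part of the source data for this trial". It ties GP records to no particular outcome.

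**The concern.** The outcomes are death and readmission anywhere, but the named source is one hospital's record. The protocol sees this difficulty at day 5, where it goes to GP records for the few patients already discharged. The same reasoning is stronger at day 30. Most participants are expected to be inpatients at day 5, and more will have gone home by day 30. Recruitment is at Major Trauma Centres and Trauma Units over a wide area, and the sample-size section (6.7.4) itself foresees patients admitted out of area and "discharged within five days to another region where GP records may not be accessible".

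Section 6.7.2 provides for marking data as missing only for questionnaires after three failed contact attempts. Nothing comparable is stated for death or readmission, so a search that finds nothing could mean either that no event occurred or that it was not visible.

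At stake are the recorded rates and absolute differences for two secondary outcomes. Section 11.4 wants readmission data to inform clinical decisions, and section 8.4 has the monitoring committee follow safety events captured as endpoints.

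**Working it through.** **1. The plan's own figure.** The protocol states no rate for day-30 death or readmission. Its only calculation is for the primary outcome, and it reproduces. Per arm, n = [1.960 × √(2 × 0.4 × 0.6) + 1.2816 × √(0.5 × 0.5 + 0.3 × 0.7)]² / 0.2² = (1.358 + 0.869)² / 0.04 = 124. That gives 248 analysed, and 248 / 0.9 = 276 recruited. The point here does not touch it.

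**2. Which source reaches which participant, for death and readmission to day 30.**

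| Participant | Named source | Event elsewhere visible? |
|---|---|---|
| Still in the recruiting hospital | Own record | Not applicable |
| Transferred to another hospital | Own record plus receiving site (6.7.3, Hospital transfers) | Yes, at the receiving site |
| Discharged home | Own record only (3, 6.7.2, 7.11) | No source named |

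**3. Size, on assumed rates.** Let m be the share of true events not visible in the recruiting hospital's record, equal in both arms and counted as no event. Then recorded rate = true rate × (1 − m). The absolute difference shrinks by (1 − m), the risk ratio is unchanged and the odds ratio moves slightly. Assume true readmission of 12% (control) and 7.2% (spirometry), with 138 per arm:

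| m | Control | Spirometry | Difference (points) | 1/difference | Odds ratio | Events missed |
|---|---|---|---|---|---|---|
| 0 | 12% | 7.2% | 4.8 | 21 | 0.569 | 0 |
| 20% | 9.6% | 5.8% | 3.8 | 26 | 0.576 | about 5 |
| 40% | 7.2% | 4.3% | 2.9 | 35 | 0.582 | about 11 |

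Odds ratio at m = 20%: (0.0576 / 0.9424) / (0.096 / 0.904) = 0.576. Events missed at m = 20%: 138 × (0.12 + 0.072) × 0.20 = 5.3.

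**4. Range.** Events missed = 276 × rate × m. For an overall true rate of 10% to 20% and m of 5% to 30%, this runs from 276 × 0.10 × 0.05 = 1.4 to 276 × 0.20 × 0.30 = 16.6.

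**5. Against the trial's precision.** For 12% against 7.2% at 138 per arm, the 95% half-width of the difference is 1.96 × √[(0.12 × 0.88 + 0.072 × 0.928) / 138] = 6.9 points. Power is about 27% even with complete capture. With a larger assumed contrast of 20% against 10%, losing 20% of events lowers power from 64% to 53%.

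**The case against.** The protocol is not silent on events outside the hospital. Transfers are covered. Safety reporting runs to day 30 (8.3), and deaths and unplanned hospitalisations are serious adverse events (8.1). The data management plan will list sources in full, and section 9.3.1 already counts GP records among them. Routine-record follow-up is a fair choice in a pragmatic trial. The rates above are assumed, the odds ratio hardly moves, and the loss of 1.0 to 1.9 points is well inside a half-width of 6.9.

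Much of this stands. Transfers need no change, and the effect on inference is small. But safety reporting covers only events that sites become aware of, so it is not a search. The general line on GP records also does not override the specific source that section 6.7.2 sets for day-30 outcomes.

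The remedy has its own limit: the out-of-area patients in section 6.7.4 are described as those whose GP records may be out of reach. For them, only the missing code helps. Nor does the protocol say that a GP record shows readmission to another hospital; that it often would is an assumption.

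A reader might infer more than the text supports:

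- **Unseen events are coded as no event.** No such rule is written. The protocol simply gives no rule.
- **Loss differs between arms because spirometry shortens stay.** Nothing in the text suggests this. If capture were 90% in one arm and 80% in the other, with equal true rates of 10% to 20%, a spurious odds ratio of about 0.87 to 0.88 would appear, but those capture figures are hypothetical.
- **Critical care is affected too.** Section 7.11 collects it for the index admission, which the recruiting or receiving hospital can see.

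**Conclusion.** The point holds for participants discharged home, and for death and readmission to day 30. For them the protocol names one hospital's record and no way to tell an unseen event from no event. If such events occur and are read as none, rates are under-counted and absolute differences shrink by the share missed: 4.8 to 3.8 points at 20% missed, or 2.9 at 40%, on assumed rates of 12% and 7.2%. With equal loss in both arms the odds ratio changes by about 0.01 and the direction of effect is not biased. The true share missed cannot be derived from the protocol.

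The primary outcome, including deaths to day 5, and the sample size are untouched. This is worth amending because the change is cheap and the protocol already uses the source; it does not threaten the trial's main conclusion.

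**What to change.** In sections 6.7.2 and 7.11, for each participant discharged before day 30:

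- Also check the GP record for death and for readmission to any hospital.
- Record on the 30-day CRF which source was used.
- Code the outcome as missing, not as no event, where no source beyond the recruiting hospital can be reached, for example for an out-of-area participant whose GP record is inaccessible.

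The source column of the trial summary should be changed to match. The transfer provision and the critical care item stay as they are.

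The cost is existing site staff time for each discharged participant, and more participants than the small number checked at day 5, plus one CRF field. GP practice details are already collected at baseline (7.9), though these are contact details and do not guarantee record access. Some outcomes will be newly recorded as missing. Because an event seen in the recruiting hospital still counts as an event, that missing group will lean towards participants without one, so its number should be reported by arm beside the rates.
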